#### Gender

Male

Female

#### Age group

18-21

22-25

26-29

30-33

34-37

38-41

42-45

46-49

50-53

54-57

58-61

62-64

#### Race/Ethnicity

White, non-Hispanic

Black, non-Hispanic

Hispanic

Other

#### Medicaid Eligibility

Disability

Low income

Other

#### AP treatment Initiation year

2002

2003

2004

2005

2006

2007

2008

2009

Diagnostic History, past year	ICD-9-CM Codes*
Depression	293.83, 296.2x, 296.3x, 296.9x, 298.0x, 300.4x, 311.xx
Anxiety	293.84, 300.0x, 300.2x, 300.3x, 308.3x, 309.21, 309.81, 313.0x, 313.2x, 313.89
Bipolar	296.xx (not 296.2x or 296.3x or 296.9x)
Substance use disorder	291.xx, 292.xx, 303.xx, 304.xx
Moderate/severe mental retardation	318.xx
HIV	042, 043, 044, 079.53, V08
Neoplasms	140.xx-239.xx (Exclude people with malignant neoplasms 140.xx-205.xx)
Diabetes	250.xx
Obesity	270.xx
Hyperlipidemia	272.0x-272.4x, 272.7x, 272.9x
White blood cell diseases	288.xx, 289.xx (exclude neutrophil d/o 288.00-288.04, 288.09, 288.1x)
Anemia	280.xx-285.xx
Drug-related dyskinesia	333.85
Hypertension	401.xx-405.xx
Ischemic heart disease	410.xx-414.xx
Pulmonary circulation diseases	415.xx-417.xx
Cardiac dysrhythmias	427.xx
Heart failure	428.xx
Cerebrovascular disease	430.xx-438.xx
Acute bronchitis and bronchiolitis	466.xx
Chronic bronchitis	491.xx
Pneumonia	480.xx-486.xx
Emphysema	492.xx
Asthma	493.xx
Appendicitis	540.xx-543.xx
Noninfectious enteritis and colitis	555.xx-558.xx
Diverticula of intestine	562.xx
Intestinal obstruction	560.xx
Chronic liver disease and cirrhosis	571.xx
Acute & chronic pancreatitis	577.0x, 577.1x
Cholelithiasis	574.xx
Acute kidney failure	584.xx
Chronic kidney failure	585.xx

Kidney infections	590.xx
Cellulitis and abscess	681.xx–682.xx
Osteoarthritis and allied disorders	715.xx
Intervertebral disc disorder	722.xx
Fractures, all sites	800.xx–829.xx
Fracture of neck of femur	820.xx
Poisoning by psychotropic medication	969.xx
Poisonings	960.xx–989.xx
Suicide and self-inflicted injury	E950-959
Intracranial injury	815.xx-854.xx
Severe cardiovascular diseases	401.0x-404.9x, 410.xx-416.xx, 425.xx-437.xx, 440.xx-447.xx
Schizophreniform	295.4x
Schizoaffective	295.7x

---

\* x indicates inclusion of any 5th digit if available for a diagnosis code.

xx indicates inclusion of any 4th and 5th digits if available for a diagnosis code.

Medication history, past year	Drug class
Psychotropic medication	
Antidepressants	SSRI/SNRI/mirtazapine, TCA and heterocyclic compounds, MAOI, trazodone-related antidepressants, bupropion
Mood Stabilizer	lithium, primary anticonvulsant, secondary anticonvulsant
ADHD medication	psychostimulants, alpha-agonists
Anxiolytic/hypnotics	benzodiazepines, GABA agonists, other newer or older anxiolytic/hypnotic
Other psychiatric medication	modafinil, oxybate, phendimetrazine, benzphetamine
OB/GYN medication	oral contraceptives, other contraception, medroxyprogesterone
Metabolic and related medication	lipid-lowering drugs, hypothyroid treatment, antithyroid agents, anorexiant
Cardiovascular medication	thiazide diuretic, ACE inhibitor/ARBs, other anti-hypertensives, other cardiovascular drugs
Respiratory/allergy medication	non-sedating antihistamines, other antihistamines, Corticosteroids, other Asthma medications, Smoking cessation
Gastrointestinal medication	histamine 2 receptor antagonists, proton-pump inhibitors, other prescription dyspepsia, Antacids, anti H pylori, phenothiazine antiemetics, Ulcerative colitis treatment
Neurologic/musculoskeletal medication	migraine treatment/prevention, NSAID, includes coxibs, narcotic analgesic, Non-narcotic analgesic (acetaminophen), Cyclobenzaprine, other skeletal muscle relaxants, other rheumatologic
Antibiotics	
Diabetic medication	
Hyperlipidemia medication	
Severe cardiovascular medication	

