### Subgroups

From the base study population described above, 5 clinical subgroups will be defined based on the presence of psychiatric diagnoses during the 30 days prior to and inclusive of the treatment change under study (index date) and who have this same diagnostic code from more than one provider to increase the validity of the diagnostic groups. The subgroups will be defined by codes to capture 1) uncomplicated schizophrenia (with schizophrenia codes from at least 2 different providers and without any diagnoses that would qualify them for the other subgroups during the 365 days prior to the index date), 2) schizoaffective disorder (ICD-9: 295.7) as the most recent schizophrenia-spectrum diagnosis, 3) depressive (ICD-9: 293.83, 296.2, 296.3, 296.9, 298.0, 300.4, 311), 4) manic (296.0, 296.4-296.8), and 5) anxiety (293.84, 300.00-300.02, 300.09, 300.20-300.23, 300.29, 300.3, 300.7, 308.0-308.9, 309.21, 309.81, 312.39, 313.0, 313.21, 313.23). These subgroups are defined to reflect the reason for the change in treatment.

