## Approach to confounding

Physicians make treatment choices in light of available clinical information and as a result there is a risk of confounding by clinical indication for the treatments under study. Our design minimizes confounding by indication by focusing on diagnostic subgroups. To further reduce confounding, we will control for a broad range of potentially relevant factors from claims histories. These factors will be identified in the 365-day period before drug initiation and used to calculate propensity scores. In addition we will conduct sensitivity analyses to estimate the extent of unmeasured confounding necessary to fully explain our observed findings and we will conduct instrumental variable analyses if a suitable instrument is identified.

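### For the depressive, manic and anxiety subgroups, Appendix 2 describes the condition that prompted the drug change only by a flag that is constant or nearly so, with no subtype, claim-count or recency covariate

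*Combined protocol and SAP*

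**What the plan says.** The Subgroups section assigns patients by the "presence of psychiatric diagnoses during the 30 days prior to and inclusive of the treatment change under study (index date") and states the purpose: "These subgroups are defined to reflect the reason for the change in treatment". The uncomplicated group must be "without any diagnoses that would qualify them for the other subgroups during the 365 days prior to the index date".

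Under Approach to confounding, restriction is the first defence: "Our design minimizes confounding by indication by focusing on diagnostic subgroups". Claims-based covariates are the second: "These factors will be identified in the 365-day period before drug initiation and used to calculate propensity scores". Under Aim 1 of the Analysis plan, treatments are compared within the five subgroups.

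Appendix 2 gives the covariates. Under "Diagnostic History, past year" there is one row each for Depression, Anxiety, Bipolar, Schizophreniform and Schizoaffective. The appendix footnote pools all further digits of a code. The service-use block holds psychiatric admissions by number, mental health emergency service, outpatient schizophrenia visits in four bands, psychotherapy and psychosocial contacts. Self-inflicted injury, psychotropic poisoning, substance use disorder and past-year psychotropic classes are also listed.

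**The concern.** Inside a subgroup, a flag built from the subgroup's own codes cannot separate or balance the treatment arms, and its standardized difference after weighting is zero whatever the true imbalance. That does no harm if other covariates describe the presenting condition. For depression, mania and anxiety, none does so specifically.

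The lists are mixed. The depressive list pools 296.2 and 296.3 with 298.0, 300.4 and 311; the anxiety list pools 300.0x, 300.2x, 300.3 and 309.81. Which drug is added may plausibly depend on the type and intensity of the episode, and these may also predict psychiatric hospitalization, the primary outcome. If so, the balance table would look perfect on the Depression row of the depressive subgroup while the arms still differed, and part of the adjusted hazard ratio would reflect the indication and not the drug.

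**Working it through.** The plan states no figure on this point, so the check is a comparison of code lists, followed by a count of episodes and an illustration.

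**1. Windows.** Subgroups use the 30 days up to and including the index date. Covariates use the 365 days before initiation. A qualifying code therefore also sets the past-year flag, unless it appears only on the index day.

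**2. Code lists, Subgroups section against Appendix 2.**

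- Depressive: the subgroup is "depressive (ICD-9: 293.83, 296.2, 296.3, 296.9, 298.0, 300.4, 311"; the flag is "293.83, 296.2x, 296.3x, 296.9x, 298.0x, 300.4x, 311.xx". The sets are identical, so the flag is 1 throughout.
- Manic: the subgroup is 296.0 and 296.4 to 296.8. The Bipolar row is all of 296 except 296.2, 296.3 and 296.9, which leaves 296.0, 296.1 and 296.4 to 296.8. Every subgroup code is inside, so the flag is 1 throughout.
- Anxiety: 300.7, 308.0 to 308.2, 308.4 to 308.9 and 312.39 are in the subgroup list but outside the flag. The flag is 0 only for patients whose past-year anxiety codes all come from these. How many there are is not stated.
- Schizoaffective: 295.7 in both places, so the flag is 1 throughout. The subgroup is a single code, so there is no code mix to adjust for.
- Uncomplicated: there is no own-diagnosis flag. Depression and Schizoaffective are 0 by definition, and Bipolar and Anxiety nearly so. Schizophreniform (295.4x) can still vary.

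The document does not say whether the score is fitted within subgroup or pooled. Either way, a flag that is constant within a subgroup cannot balance arms there.

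**3. What else describes the condition.** The only diagnosis-specific visit count is for schizophrenia. Admissions, emergency use, psychotherapy and self-harm are general past-year measures. The psychotropic classes relate to the condition, but Data source and cohort identification bars other psychotropics for at least 90 days before the index date, so these rows reflect only earlier use. No covariate isolates the 30 days that define the subgroups.

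**4. Share of episodes (Table 5).**

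- Uncomplicated: 27,005 + 9,954 + 25,061 + 12,248 = 74,268
- Schizoaffective: 6,393 + 4,734 + 9,692 + 3,681 = 24,500
- Depression: 2,192 + 1,296 + 4,646 + 1,199 = 9,333
- Mania: 1,580 + 2,107 + 840 = 4,527
- Anxiety: 611 + 1,110 + 1,099 = 2,820

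The total is 115,448. The first two hold 98,768 / 115,448 = 86%; the three subgroups with the main gap hold 16,680, or 14%.

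**5. Illustration, all inputs assumed.** Let a severity marker have prevalence p1 and p0 in the two arms and multiply admission risk by RR. If it is left unadjusted, the risk ratio is multiplied by [1 + p1(RR − 1)] / [1 + p0(RR − 1)]. With p0 = 0.20:

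| p1 | RR = 1.5 | RR = 2 |
|---|---|---|
| 0.30 | 1.15/1.10 = 1.045 | 1.30/1.20 = 1.083 |
| 0.40 | 1.20/1.10 = 1.091 | 1.40/1.20 = 1.167 |
| 0.50 | 1.25/1.10 = 1.136 | 1.50/1.20 = 1.250 |

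At an assumed 25% one-year admission risk, 0.25 × (factor − 1) gives 1.1, 2.3 and 3.4 points for RR = 1.5, and 2.1, 4.2 and 6.25 points for RR = 2. These are upper values, because the general proxies would absorb part.

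**The case against.** The best reply is that a constant flag is what restriction is meant to produce. The plan controls indication by comparing like with like, and deleting the flag would change nothing. That stands: the flag is not a mistake, and the point reduces to a request for additional covariates.

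A reader might infer that the score ignores the type and intensity of the presenting condition in every subgroup. The documents do not support that. Uncomplicated schizophrenia has no own-diagnosis flag, and schizoaffective disorder is one code. The banded schizophrenia visit count grades the presenting condition in the uncomplicated group and plausibly in the schizoaffective group, since schizophrenia is defined as ICD-9 295, which includes 295.7. In the other three subgroups, admissions by number, emergency use, psychotherapy, self-harm, comorbid diagnoses and earlier drug classes give some indirect adjustment.

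The plan has other safeguards. The array analysis shows how strong an unmeasured confounder would have to be, but these variables are in the claims and can be adjusted for directly. The instrumental variable analysis depends on finding an instrument. Requiring the diagnosis from more than one provider supports its validity and sets some floor on coding intensity, but does not grade severity above that floor.

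It can also be said that nothing in the documents shows that code group or claim count tracks severity. That is fair, and it is a reason to treat this as an inexpensive improvement and not as the repair of a demonstrated bias.

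**Conclusion.** The point holds in a limited form. In the depressive and manic subgroups the own-diagnosis flag is constant, index-day-only coding aside; in the anxiety subgroup it is probably near-constant, subject to unreported code frequencies. Appendix 2 has no condition-specific subtype, count or recency variable for these conditions, so what prompted the drug change is adjusted only through general past-year proxies. In the schizoaffective and uncomplicated subgroups the gap is mainly recency.

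The tempting further step is to say that the hazard ratios are biased by a known amount. They may not be. The factors of 1.05 to 1.25 rest wholly on assumed prevalences and risk ratios, and the conversion to points adds an assumed admission risk. The 5.0-point difference under Sample size is a power figure, not a tolerance for bias, so setting the illustration against it proves nothing. The document gives no severity distribution from which a size could be derived.

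**What to change.** In Appendix 2, for the depressive, manic and anxiety subgroups, add covariates taken before the index date from the claims already used to assign subgroups:

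- the code group of the most recent qualifying claim, with fifth-digit severity where coded;
- the number of claims for the condition in the past 30 days and in the past 365 days;
- whether the diagnosis first appeared in the past 30 days.

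For the schizoaffective and uncomplicated subgroups, add a count of 295 claims in the past 30 days. Report standardized differences on all of these after weighting, by subgroup.

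The cost is an appendix edit and modest programming on data already read. The downside is a few more score terms in the smallest cells, such as the 611 episodes in the anxiety column of Table 5, where rare code groups can be combined. The expected gain is less confounding; the documents give no basis for claiming a gain in power.

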## Goal

More than half of individuals diagnosed with schizophrenia have an incomplete response to a prescribed antipsychotic medication. In spite of the high proportion of patients who experience an incomplete response, little is known about the comparative effectiveness of treatment options that are commonly used in this situation. The proposed research question “For patients with schizophrenia who have persistent, emergent or recurrent psychiatric symptoms in spite of antipsychotic treatment, what are the medication treatment options and what are their comparative benefits and risks?” thus has considerable public health importance is relevant to a large proportion of the approximately 3 million individuals with schizophrenia in the U.S. specifically, the project seeks to achieve the following aims:

1. Within five clinically important schizophrenia subgroups, compare the effectiveness and safety of alternative medication strategies beyond antipsychotic monotherapy.
2. Within the five subgroups, explore whether the comparative effectiveness and safety of alternative treatment strategies varies according to patient age and presence of a substance use disorder.
3. Conduct instrumental variable and sensitivity analyses to examine the robustness of the treatment effectiveness results that are based on propensity score methods.

The project will yield unbiased, generalizable, and patient-centered information on the comparative effectiveness and safety of alternative medication strategies for patients with schizophrenia who have an incomplete response to

standard antipsychotic monotherapy. New information will be generated regarding the comparative effectiveness and safety of commonly used but poorly understood second-line medication treatment strategies. We will compare the effectiveness of these medication treatment strategies for schizophrenia in five subgroups based on presenting symptoms and syndromes that lead to initiation of a new psychotropic strategy: 1) schizoaffective, 2) depressive, 3) anxiety, 4) manic, and 5) uncomplicated schizophrenia.

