### Secondary

We will also investigate time to index treatment discontinuation, time to introduction of another psychotropic medication, psychiatric emergency department visits, all-cause hospitalization, and death.

We will investigate adverse effects of medications including incidence of major cardiovascular events and diabetes mellitus.

Outcomes	
Death	Date of death will be defined by the Social Security Death Master File.
Psychiatric Hospitalization	Hospital claims will define inpatient admissions with a first listed mental disorder diagnosis (ICD-9:290-310). High levels of agreement between diagnoses in inpatient medical records and inpatient claims have been reported for several mental disorder groups, including schizophrenia (100.0%), major mood disorders (98.7%), alcohol dependence (97.8%), and drug dependence (96.4%). 
Psychiatric ED Visits	Emergency department claims are a reliable source of diagnostic information in relation to medical records and a valid source of illness severity information.  Emergency department visits in which the first listed diagnosis is a mental disorder (ICD-9-CM: 290-319) will be defined as emergency department mental health visits.
Self-Injurious Behavior	Deliberate self-harm will be defined by an E-code of E950-E958, excluding late effects of deliberate self-harm (E959), on any inpatient, emergency department, or outpatient claim. High positive predictive values have been reported. 
Diabetes Mellitus	One or more claims with a physician diagnosis of diabetes will define diabetes mellitus. Using self-reported diabetes status as the criterion standard, $\geq 1$ physician claim with any diagnosis of diabetes or a diabetes complication (ICD-9 codes: 295.00-2950.93, 357.2, 362.0-362.02, 366.41) has acceptable sensitivity (68.5%) and specificity (96.9%), and (kappa=0.76).  Sensitivity of 90% and specificity of 93% with self-reported diabetes. 
Cardiovascular Events:	Acute myocardial infarction (AMI) (ICD-9-CM: 410) or stroke (430-438, except 435) will be defined by diagnostic codes on inpatient claims of $\geq 3$ days in duration.  With this AMI definition 75% met criteria for definite or probable AMI on independent review of cardiac biomarkers, electrocardiograms, presenting symptoms, and medical history, and an additional 12% had a suspected AMI. 

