### *Propensity score estimation and application*

Propensity score methods involve two steps: estimation of the propensity scores and application of the propensity score. Estimation of the propensity scores involves decisions about which covariates to include in the prediction model of the propensity scores and what form the model should take. We will use expert opinion to select the variables to include in the propensity score. To estimate the propensity scores we will first use logistic regression including all baseline predictors occurring prior to treatment assignment. In addition, we will augment our analysis with another non-parametric method for building the propensity score model such as a generalized boosting algorithm implemented with regression trees. We will assess the sensitivity of our results to the choice of the propensity score model.

For the application of the propensity scores, we will use weighting by the odds to estimate the average treatment effect on the treated sample and weighting by the inverse probability of treatment weights to estimate the average treatment effect in the population.

We will examine the covariate balance using standardized differences in covariate means across the treatment groups after weighting, and address any significant imbalances.

**AIM 2 Heterogeneity of Treatment Effects:** Within the five subgroups, explore whether the comparative effectiveness and safety of alternative treatment strategies varies according to patient age and presence of a substance use disorder.

We will use similar Cox model techniques for the HTE analyses. First we will assess interaction of age and substance use variables with treatment. If such interactions are found, we will then perform analyses examining alternative treatment strategies stratified by age group or substance use.

The rationale for investigating patient age as a moderator of antipsychotic treatment effects follows from evidence that individuals early in the course of psychosis may respond differently to medications than people with more chronic illness. The rationale for investigating comorbid diagnosis of a substance use disorder as a moderator of treatment effects follows from evidence that people diagnosed with schizophrenia and comorbid substance use disorders respond more poorly to antipsychotic medications than those without comorbid substance use disorders.

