## Appendix 2: Variables included in the Propensity Score

### Demographics

---

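### The plan's only code list for substance use disorder omits the ICD-9-CM 305 abuse codes, leaving avoidable residual confounding in Aim 1 and possibly diluting the Aim 2 interaction

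*Combined protocol and SAP*

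**What the plan says.** Aim 2, in the Goal section, asks whether comparative effectiveness and safety "varies according to patient age and presence of a substance use disorder". The Aim 2 paragraph of the Analysis plan gives the procedure: "First we will assess interaction of age and substance use variables with treatment". Stratified analyses follow only if an interaction is found. The rationale there refers to "comorbid diagnosis of a substance use disorder as a moderator of treatment effects". Nothing restricts this to dependence, and no codes are given.

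The only codes are in Appendix 2, headed "Variables included in the Propensity Score". In its past-year diagnostic history table, the substance use disorder row reads "291.xx, 292.xx, 303.xx, 304.xx". The table footnote says that "xx indicates inclusion of any 4th and 5th digits if available for a diagnosis code", so the wildcard extends codes within a category and cannot bring in category 305.

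Approach to confounding sets the covariate look-back at 365 days before drug initiation. The Outcomes table counts as a psychiatric hospitalization any admission whose first-listed code lies in 290-310, a range that contains 305.

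**The concern.** The label and the codes do not match. That category 305 holds non-dependent abuse of alcohol and drugs comes from the coding system the plan uses; the documents do not spell it out. On that footing, a patient with repeated alcohol, cannabis or cocaine abuse claims and no code in 291, 292, 303 or 304 is recorded as free of a substance use disorder.

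Two things are at stake.

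- **Aim 1.** The row is expressly a propensity-score covariate. The treatments compared include starting a benzodiazepine, and a known history of substance abuse could plausibly influence that choice. It could also plausibly affect the risk of psychiatric admission. Weighting on a variable that misses these patients leaves that imbalance unadjusted, although the claims needed to measure it are in the data.
- **Aim 2.** If the moderator uses the same list, the no-disorder stratum contains patients with a disorder. This can pull the two strata together, and stratified results appear only if the interaction is detected.

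**Working it through.** **1. The plan's own figure.** The documents give no power calculation for the interaction and no prevalence of substance use disorder. The nearest figure, in Sample size, is the main-effect calculation for the depression subgroup: 1,534 patients per group, a 5.0-point difference, two-sided alpha 0.05, at least 80% power. No base rate is stated. A two-proportion test with pooled variance gives 80.0% for 40% vs 45%, 84.1% for 30% vs 35%, and 79.1% for 47.5% vs 52.5%. The figure reproduces, and the omitted codes do not affect it.

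**2. Contamination of the no-disorder stratum, if Aim 2 uses the Appendix 2 list.** Let P be the true prevalence and s the share of true cases with abuse codes only. Both are assumptions: P 20-50%, s 10-50%. With no false positives, the share of true cases in the no-disorder stratum is

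c = Ps / (Ps + 1 − P).

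Example: P = 0.4 and s = 0.3 give 0.12 / (0.12 + 0.60) = 0.167.

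**3. Effect on the interaction.** Let f be the effect modification in abuse-only patients as a fraction of that in patients with a listed code. On an additive scale (for a Cox model, roughly the log hazard ratio):

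- listed codes: contrast = 1 − cf
- list with abuse codes added: contrast = (1 − s) + sf

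The listed codes give the smaller contrast only if f > s / (s + c).

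| P | s | c | Contrast with listed codes, f = 1 | Break-even f |
|---|---|---|---|---|
| 20% | 10% | 2.4% | 0.976 | 0.80 |
| 20% | 50% | 11.1% | 0.889 | 0.82 |
| 40% | 30% | 16.7% | 0.833 | 0.64 |
| 50% | 10% | 9.1% | 0.909 | 0.52 |
| 50% | 50% | 33.3% | 0.667 | 0.60 |

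At P = 40% and s = 30%, listed versus broader codes give 0.83 vs 1.00 when f = 1, 0.92 vs 0.85 when f = 0.5, and 1.00 vs 0.70 when f = 0.

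**4. Power for the interaction if f = 1.** Take N = 1,534 per arm, an outcome rate of 0.5 and a share q classed as having the disorder. The standard error of the difference in risk differences is √[0.5 / (N q(1 − q))]. At q = P = 0.40 this is √[0.5 / (1,534 × 0.24)] = 0.0369, so 80% power needs 2.80 × 0.0369 = 10.3 points. With the listed codes, q becomes P(1 − s) and the contrast becomes 10.3(1 − c):

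- s = 10%: q = 0.36, 9.7 points, power 73%
- s = 30%: q = 0.28, 8.6 points, power 57%
- s = 50%: q = 0.20, 7.7 points, power 40%

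The broader list also splits the sample more evenly, so its break-even for power is lower than for size. At P = 40% and s = 30%, solving (1 − 0.167f)√(0.28 × 0.72) = (0.7 + 0.3f)√(0.40 × 0.60) gives f of about 0.48.

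**5. Aim 1.** The size of the residual confounding cannot be computed. It needs the abuse-only prevalence in each treatment group and the association with the outcome, and the documents give neither.

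**The case against.** - **The moderator is not tied to this list.** Appendix 2 lists propensity-score variables, and Aim 2 names no codes. This stands. A reader might infer that abuse-only patients are definitely placed in the wrong Aim 2 stratum; the documents support only that they would be if the list is reused. The alternative is a prespecified moderator with no definition, which also needs correcting.
- **Dilution is not certain.** This stands. If abuse-only patients behave more like patients without a disorder, the narrow list loses little, and widening it could itself shrink the contrast.
- **A real interaction could still be found.** This stands for the large subgroups. In uncomplicated schizophrenia, 70% of the 25,061 antidepressant episodes is about 17,543 patients per arm. By the formula in step 4, a 5-point interaction has about 99.6% power with complete coding at P = 40%. It has about 94% at 16.7% contamination and about 77% at the 33% corner. The loss matters mainly in the small subgroups.
- **Aim 1 is not wholly uncontrolled.** This stands. Psychiatric admissions, mental health emergency use, poisonings, self-injury, liver disease and HIV are in the score, and analyses for unmeasured confounding are planned. These are partial proxies and after-the-fact bounds. They do not replace a confounder that the claims record directly.
- **The narrow list may be deliberate.** The agreement figures in the Outcomes table are for alcohol dependence (97.8%) and drug dependence (96.4%), with none for abuse codes. That is a fair reason to keep the narrow definition as well. But the plan neither says so nor labels the row as dependence.
- **The outcome range proves nothing.** A reader might take the inclusion of 305 in 290-310 as a contradiction. It is not: 301, 302, 306 and 307 also lie in that range without a matching covariate, and an outcome range need not mirror a covariate list.

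**Conclusion.** The point holds for Aim 1 as the plan is written: patients with abuse codes only are treated in the propensity score as having no substance use disorder. The resulting residual confounding is avoidable, but its direction and size are not shown. For Aim 2 the point is conditional. It requires that the Appendix 2 list defines the moderator, and that abuse-only patients share enough of the effect modification.

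Under the assumed ranges, contamination of the no-disorder stratum is about 2% to 33%. The interaction shrinks by that fraction only if f = 1. At the corners of those ranges the narrow list gives the smaller contrast only when f exceeds roughly 0.52 to 0.82. The firmer statement, that the interaction is diluted by a known amount, is not supported: the documents contain neither the prevalence, nor the abuse-only share, nor how these patients respond. Patients with a 305 code plus any listed code are captured either way. This is a correctable mismatch between label and codes that should be put right before analysis; it does not invalidate the design.

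**What to change.** 1. In Appendix 2, add 305.0x and 305.2x-305.9x (leaving out 305.1, tobacco) to the propensity score, preferably as a separate abuse-only indicator beside the existing row. The score can then weight the two groups differently.
2. In the Aim 2 paragraph of the Analysis plan, state that the moderator is any of 291, 292, 303, 304 or these abuse codes in the 365 days before t0.
3. Report the dependence and substance-induced definition (291, 292, 303, 304) as a prespecified sensitivity analysis for the Aim 2 interaction.

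The cost is one code-list edit, one extra covariate and one repeated interaction analysis, all from claims already in the data. The downside is a broader and possibly milder disorder stratum, and some patients would enter it on abuse claims for which the plan cites no agreement figures. That could reduce the contrast if abuse-only patients respond more like those without a disorder, which is why both definitions should be reported.
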